7.3 CLINICAL LABORATORY TESTS

Blood and urine samples will be obtained for assessment of clinical laboratory parameters. Clinical laboratory assessments (hematology, chemistry, urinalysis, coagulation) will be performed on the visits as described in the schedule of study assessments and procedures in protocol section 22.2.

Clinical laboratory parameters at all scheduled visits and the change from baseline to post baseline visits will be summarized using appropriate summary statistics by dose groups. Categorical urinalysis parameters will be summarized using count and percentages by dose cohorts for each scheduled visit.

Separate summary tables for each dose cohort and overall will be presented for the laboratory results that are marked as abnormal clinically significant by the investigator.

All clinical laboratory results will also be listed. Laboratory values that are outside the normal range will be flagged in a participant data listing.

Separate summary table and listing will be presented for the booster phase.

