Baseline serology will be drawn for detection of antibodies against SARS-CoV-2, HIV, HBV and HCV at the local lab. The results of SARS-CoV-2 tests that were performed up to 7 days before Visit 0 are acceptable. The results of negative HIV tests that were performed up to 30 days before Visit 0 are acceptable. A positive HIV test obtained by ELISA will have to be confirmed by a second method (e.g. Western blot or PCR) [blood (for all tests): 5 mL]. In addition, an HLA typing test will be done at Screening (20 mL)

Laboratory values will be evaluated according to the Toxicity Grading Scale for Healthy Adult and Adolescent Volunteers Enrolled in Preventive Vaccine Clinical Trials (FDA). For the individual toxicity criteria refer to section 22.4.

Laboratory assessments for which no severity grading is described in section 22.4 are graded as described in Section 15.2.1.1 upon the Investigator's judgement.

The Investigator's assessment of each abnormal laboratory value, including its clinical significance, is to be recorded in the eCRF:

- Abnormal laboratory assessments that are considered clinically relevant, in the opinion of the Investigator, need to be documented as unsolicited AEs and assessed further for severity according to the toxicity grading scale provided in Section 22.4, causality and other assessments done for unsolicited AE (see Section 15.2.1).
- Abnormal laboratory assessments that are considered a symptom of an underlying AE or part of a syndrome that is reported as AE (e.g. presence of blood cells in urine in a person diagnosed with urinary tract infection) do NOT additionally need to be documented as unsolicited AE, but a respective comment should be added to the underlying AE.

Additional tests and other evaluations required to establish the significance or aetiology of an abnormal laboratory result or to monitor the course of an AE should be obtained when clinically indicated. Any abnormal value that persists should be followed at the discretion of the Investigator.

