### **16.4.3 Secondary Endpoints**

#### **16.4.3.1 Secondary Safety Endpoints**

The number and percentage of Participants with unsolicited AEs (including those with clinically relevant laboratory parameter changes), related AEs, AESIs and SAEs will be presented for each study arm, overall, by system organ class/preferred term and by severity. Differences between study groups will be assessed for significance using Fisher's exact (Fisher-Freeman-Halton) test, whereby a significant overall test will be amended by pair-wise tests, and 95% confidence interval (CI) will be presented for all AE rates.

The number and percentage of Participants with abnormal laboratory parameters will be presented for each study arm, overall and by parameter.

Further details will be provided in the Statistical Analysis Plan (SAP).

All analyses of safety data will be based on the SAS.

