PT – increase by factor	1.0–1.10 x ULN	1.11–1.20 x ULN	1.21–1.25 x ULN	> 1.25 ULN
PTT (aPTT) – increase by factor	1.0–1.2 x ULN	1.21–1.4 x ULN	1.41–1.5 x ULN	> 1.5 x ULN
Fibrinogen increase - mg/dL	400–500 d	501–600	> 600	–
Fibrinogen decrease - mg/dL	150–200 d	125–149	100–124	< 100 or associated with gross bleeding or disseminated intravascular coagulation

AE=adverse event; ALT=alanine aminotransferase; AST=aspartate aminotransferase; aPTT=activated partial thromboplastin time; CRP=C reactive protein; ESR=erythrocyte sedimentation rate; FDA=Food and Drug Administration; PT=prothrombin time; SAE=serious adverse event; ULN=upper limit of normal; WBC=white blood cell

a In case the laboratory's normal ranges and absolute Grade 1 limits overlap, Grade 1 limits will prevail, i.e. the value will be classified as Grade 1 abnormality even if it is within central laboratory normal ranges. Values between the central laboratory normal ranges and absolute Grade 1 limits will be reported as no abnormality (Grade 0).

b The clinical signs or symptoms associated with laboratory abnormalities might result in characterization of the laboratory abnormalities as potentially life threatening (Grade 4). For example, a low sodium value that falls within a grade 3 parameter (125–129 mE/L) should be recorded as a grade 4 hyponatremia unsolicited AE if the Participant had a new seizure associated with the low sodium value.

c As neither the FDA Scale nor the Division of AIDS Table for Grading the Severity of Adult and Pediatric Adverse Events (December 2004) provide any grading for haematocrit, erythrocyte count, monocytes, Basophils, ESR and CRP, these will only be analysed as 'outside normal range', as determined by central laboratory standards and graded as described in Section 15.2.1.1 upon Investigator's judgement.

d Central laboratory values should be adjusted to FDA toxicity grading scale. Specifically, if central laboratory reference range is more stringent than FDA toxicity grading scale the central laboratory values should be reported as no abnormality (Grade 0). Similarly, if laboratory values are within the central laboratory normal reference range, but fall into FDA toxicity grading scale, the values should be reported as indicated by the FDA toxicity grading scale.

e Any Grade 4 abnormal laboratory value should be reported as an SAE (see Section 16.1.2).

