14.2.1.23	Summary of Unsolicited AEs by Causality until day of Data Cut for Day 106 analysis	Safety	No	Yes	No
14.2.1.24	Solicited Injection Site Reactions Within 7 Days After Booster Vaccination	Safety (Booster)	No	No	Yes
14.2.1.25	Solicited Systemic Reactions Within 7 Days After Booster Vaccination	Safety (Booster)	No	No	Yes
14.2.1.26	Solicited Injection Site Reactions Within 7 Days After Booster Vaccination By Maximum Severity	Safety (Booster)	No	No	Yes
14.2.1.27	Solicited Systemic Reactions Within 7 Days After Booster Vaccination By Maximum Severity	Safety (Booster)	No	No	Yes

14.2.1.28	Duration of Solicited Injection Site Reactions after Booster Dose	Safety (Booster)	No	No	Yes
14.2.1.29	Duration of Solicited Systemic Reactions after Booster dose	Safety (Booster)	No	No	Yes
14.2.1.30	Overall Summary of Unsolicited Adverse Events (Booster Phase)	Safety (Booster)	No	No	Yes
14.2.1.31	Summary of Unsolicited AEs Up to Visit 9 (Booster Phase)	Safety (Booster)	No	No	Yes
14.2.1.32	Summary of Treatment Related Unsolicited AEs Up to Visit 9 (Booster Phase)	Safety (Booster)	No	No	Yes
14.2.1.33	Summary of Serious Unsolicited AEs Up to Visit 9 (Booster Phase)	Safety (Booster)	No	No	Yes
14.2.1.34	Summary of AESI Up to Visit 9 (Booster Phase)	Safety (Booster)	No	No	Yes
14.2.1.35	Summary of Unsolicited AEs Up to Visit 10 (Booster Phase)	Safety (Booster)	No	No	No
14.2.1.36	Summary of Treatment Related Unsolicited AEs Up to Visit 10 (Booster Phase)	Safety (Booster)	No	No	No
14.2.1.37	Summary of Serious Unsolicited AEs Up to Visit 10 (Booster Phase)	Safety (Booster)	No	No	No
14.2.1.38	Summary of AESI Up to Visit 10 (Booster Phase)	Safety (Booster)	No	No	No
14.2.1.39	Summary of Unsolicited AEs by Maximum Severity Up to Visit 9 (Booster Phase)	Safety (Booster)	No	No	Yes
14.2.1.40	Summary of Unsolicited AEs by Closest Causality Relationship Up to Visit 9 (Booster Phase)	Safety (Booster)	No	No	Yes
14.2.1.41	Summary of Unsolicited AEs by Maximum Severity Up to Visit 10 (Booster Phase)	Safety (Booster)	No	No	No
14.2.1.42	Summary of Unsolicited AEs by Closest Causality Relationship Up to Visit 10 (Booster Phase)	Safety (Booster)	No	No	No
14.2.2.1	Hematology: Summary and Change from Baseline	Safety	No	No	No
14.2.2.2	Hematology: Abnormal Clinically Significant Results	Safety	No	No	No
14.2.2.3	Biochemistry: Summary and Change from Baseline	Safety	No	No	No

14.2.2.4	Biochemistry: Abnormal Clinically Significant Results	Safety	No	No	No

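### The SAP narrows the protocol's laboratory abnormality analysis to investigator-flagged results without declaring the change, so participants with unflagged Grade 1–3 or out-of-range values are not counted by dose group

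*SAP*

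**What the plan says.** Protocol 16.4.3.1 makes two separate laboratory commitments. Unsolicited AEs are tabulated "including those with clinically relevant laboratory parameter changes". In addition, "The number and percentage of Participants with abnormal laboratory parameters will be presented for each study arm, overall and by parameter". Protocol 15.7 says how values are judged: "Laboratory values will be evaluated according to the Toxicity Grading Scale", with the criteria in section 22.4. For parameters that the scale does not grade, footnote c of 22.4 says "these will only be analysed as" outside the normal range.

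SAP 7.3 plans descriptive summaries: "Clinical laboratory parameters at all scheduled visits and the change from baseline to post baseline visits will be summarized" by dose group, with counts and percentages for categorical urinalysis. Its abnormality tables, by dose cohort and overall, cover only "laboratory results that are marked as abnormal clinically significant by the investigator". Values outside the normal range are flagged in a listing. The index in SAP 13.2 matches this, with titles such as "Hematology: Abnormal Clinically Significant Results".

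Protocol 16.4 says that a change to the planned analyses will be described and justified in the SAP. SAP 13.1 declares one change, the dropped stratification by screening serostatus. It says nothing about laboratory data.

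**The concern.** The protocol treats abnormal values as a wider set than clinically relevant ones: it counts the second as AEs and then asks for the first separately. The SAP tabulates only the narrower set, so a safety comparison between arms that the protocol specifies would not be made if the SAP is followed as written.

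This is a first-in-human study of three dose levels, with optimal dose as a secondary objective. A rise with dose in the number of participants crossing a mild, moderate or severe laboratory threshold, each value judged unimportant on its own, is the kind of pattern that a count by arm is meant to show. Under the SAP that count depends on an investigator's judgement of each value, not on the protocol's scale.

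**Working it through.** The point rests on no sample size, power or alpha figure, so there is no stated figure to reproduce. The check sets the provisions side by side.

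1. **Which set is promised.** Protocol 16.4.3.1 lists clinically relevant laboratory changes under unsolicited AEs and abnormal parameters in a sentence of their own. If the two were the same set, the second sentence would add little.

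2. **What abnormal means.** 16.4.3.1 does not define it, but 15.7 and 22.4 do. Section 22.4 grades 17 analytes:
   - haematology, 6: haemoglobin, WBC, neutrophils, lymphocytes, eosinophils, platelets;
   - chemistry, 8: creatinine, sodium, potassium, calcium, AST, ALT, alkaline phosphatase, bilirubin;
   - coagulation, 3: PT, aPTT, fibrinogen.

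   6 + 8 + 3 = 17. Six more parameters (haematocrit, erythrocytes, monocytes, basophils, ESR, CRP) are assessed only against the normal range.

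3. **What the SAP tabulates.** Table 14.2.2.x has eight abnormality tables: .2, .4, .6 and .9 for the main study, and .11, .13, .15 and .18 for the booster phase. All eight are restricted to clinically significant results. The index has no table by toxicity grade, no shift table and no table of all abnormal values. SAP 7.3 does not mention the laboratory grading scale.

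4. **Whether the listing fills the gap.** The listing flags values outside the normal range. Footnotes a and d of 22.4 use a different rule: grade limits prevail over the laboratory range. A value inside the range but in a Grade 1 band is Grade 1, and a value outside the range but short of Grade 1 is Grade 0. The flag can therefore miss values the protocol grades and mark values it does not. A listing also gives no count by arm.

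5. **What is captured elsewhere.**

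| Type of result | Where it appears |
|---|---|
| General shift, or an extreme value | Summary tables by dose group and visit; SAP 5.1 gives mean, SD, median, minimum and maximum |
| Categorical urinalysis | Counts and percentages, table 14.2.2.7 (booster 14.2.2.16) |
| Judged clinically relevant | AE tables, including by severity (protocol 15.7, SAP 7.2.1) |
| Grade 4 | Reported as SAEs (22.4, footnote e) |
| Grade 1–3 or out of range, not judged clinically significant | Listing; no count of participants by dose group |

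   The last row is the gap.

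6. **Illustration only.** The documents give neither abnormality rates nor flagging rates. Assume a graded abnormality in 10% of one arm of 50 and 30% of another, with investigators flagging the same share q in both. The expected count in the SAP table is 50 × rate × q.

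| q | Arm at 10% | Arm at 30% | Difference shown |
|---|---|---|---|
| 1.00 | 5 | 15 | 10 |
| 0.50 | 2.5 | 7.5 | 5 |
| 0.25 | 1.25 | 3.75 | 2.5 |
| 0.10 | 0.5 | 1.5 | 1 |

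   The contrast shrinks in proportion to q. This shows the mechanism and is not an estimate for this trial.

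**The case against.** The strongest reply is that little is hidden. Minimum and maximum by dose group and visit expose a marked value, and the median exposes a general shift. Clinically relevant values reach the AE tables with a severity grade, Grade 4 values reach the SAE tables, and clinically relevant Grade 3 laboratory abnormalities also feed a study-stopping criterion in protocol 10.6.2. This stands, and it limits the gap to the last row of the table in step 5. It does not restore the missing count: an extreme shows that one participant was far out, not how many crossed a threshold in each arm.

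A second reply is that no protocol sentence asks for a table by grade, and that 16.4.3.1 leaves further details to the SAP. The first part is right. The use of grades is inferred from 15.7 read with footnote c of 22.4, because saying that six parameters are analysed only against the range implies that the others are analysed by grade. The n (%) abnormal by arm and parameter needs no inference, and detailing an analysis is different from replacing its population.

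A reader might also infer that laboratory data are left out altogether, because every laboratory table is marked No for all three interims. The documents do not support that. The index columns cover interims only, protocol 16.5 plans a final analysis after Visit 10, and vital signs, physical examination and medications are marked the same way. This is staging.

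**Conclusion.** The point holds as an undeclared narrowing of a protocol-specified safety analysis. It should be corrected before the final analysis. What is missing is the number and percentage of participants, by dose group, with Grade 1–3 or out-of-range values not judged clinically significant, across the 17 graded analytes and the six assessed against the range. The number of participants affected cannot be estimated from the documents.

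Three stronger readings go too far. A dose-related laboratory shift would not be visible in listings alone, since the summary statistics and the AE and SAE routes remain. Flagging may differ between sites, but nothing in the documents shows that it does. And the missing tables cannot now affect the dose: protocol 8.5 records that the high dose was already selected on Day 36 data.

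The conclusion assumes that the SAP's clinically significant flag and the protocol's clinically relevant judgement are in practice the same decision, and that abnormal in 16.4.3.1 takes its meaning from 15.7 and 22.4.

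**What to change.** Add to SAP 7.3 and the table index, for the final analysis:

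- n (%) of participants with any post-vaccination abnormal value, by parameter, dose group and overall, using the worst section 22.4 grade where one exists and outside normal range otherwise;
- the same for the booster phase, relative to Visit 7.

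Keep the clinically significant tables as a supplement. Shift tables from baseline grade, and inclusion in the third interim, are optional. If the sponsor prefers the narrower analysis, SAP 13.1 should declare and justify it.

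The data are already collected, so the cost is a few tables plus written derivation rules for the less simple parts of 22.4: overlap between normal ranges and grade limits (footnotes a and d), clinical signs that can raise a grade (footnote b), and bilirubin grading that depends on liver tests. The benefit is a complete laboratory safety comparison by dose in the final report.

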7.4 VITAL SIGNS

Vital signs will include body temperature (°C) measured orally, pulse rate (beats/min), and systolic and diastolic blood pressure (mmHg) while seated and at rest.

Vital signs will be measured at Screening (Visit 0), Visit 5 Day 106 and Visit 6 Day 208. At both vaccinations visits (Visit 1 Day 1 and Visit 3 Day 22) these data will be recorded prior to vaccination and in addition, pulse rate and blood pressure will be assessed after vaccination while seated and at rest after a 30-minute observation period. In addition, for the sentinel dosing group, pulse rate and blood pressure will be recorded shortly before discharge from study site (3 hours or respectively, 60 min minutes after vaccination).

Tables presenting descriptive statistics for the observed data at each scheduled visit and the corresponding change from baseline at the post-baseline visits will be presented for each dose cohort. All vital signs data will also be listed.

Separate Summary table and listing will be presented for the booster phase.

7.5 PHYSICAL EXAMINATION

At the screening (Visit 0), a physical examination will be performed on the following body systems being described as normal or abnormal: general appearance, head and neck, eyes and ears, nose and throat, chest, lungs, heart, abdomen, extremities and joints, lymph nodes, skin, and neurological. At

subsequent visits, and prior to discharge after vaccinations on Visits 1 and 2, a symptom-driven physical examination will be performed, i.e. only in case a symptom is reported by the participant, an assessment of the affected body system(s) will be performed.

Physical examination results (Normal, Not clinically significant, Clinically significant) will be summarized for all body systems examined at all scheduled visits by dose cohorts. Physical examination results will also be listed. Separate summary table and listing will be presented for the booster phase.

7.6 SERUM/URINE PREGNANCY TEST

For women of childbearing potential, a urine sample and a serum test for pregnancy will be performed at screening and before the 1st and 2nd vaccination. In addition, a urine pregnancy test will be done prior to vaccination at Visit 7. All results will be presented in participant data listings.

8 IMMUNOGENICITY ANALYSES

Immunogenicity samples (10ml) will be drawn for SARS-CoV-2-specific neutralizing antibody titre evaluation using wild-type virus microneutralization assay (WT-MNA) and binding IgG antibody titre evaluation by ELISA. In addition, a blood sample [approx. 50mL] will be collected to isolate PBMCs from all participants except sentinel participants for future investigation of cellular immune responses to VLA2001.

Serum samples to measure SARS-CoV-2 neutralizing antibody levels will be collected from participants on Day 1 (prior first vaccination), Day 8, Day 22 (prior second vaccination), Day 36, Day 106 and Day 208. An authorized laboratory will measure virus specific neutralizing antibodies to SARS-CoV-2 using wild-type virus microneutralizing assay (WT-MNA). In brief, infectious virus is incubated with sera. Virus susceptible cell monolayers are exposed to the test sera/virus mixture. Patches of infected cells (microplaques) are detected via an antibody pair specific for the SARS-CoV-2 RBD Spike protein and visualised using colored substrate. Neutralizing titer of test sera is expressed as ND₅₀; serum dilution at where 50% of virus is neutralized. The Part A Day 36 analysis was performed with values below the limit of quantification of the WT-MNA (ND₅₀=58; i.e titre <58) before the WT-MNA was fully validated and LLOQ values were replaced with a value of 29 (i.e LLOQ/2=29). All subsequent analyses are performed with values below the limit of quantification of the fully validated WT-MNA (ND₅₀=62; i.e titre <62) and values lower than LLOQs will be replaced by 31 (LLOQ/2= 31). For results given as e.g. ND₅₀>SDUL reported value will be replaced with the highest sample dilution tested (SDUL) in all analyses..

In addition to the functional assays, samples are analysed for IgG against SARS-CoV-2 by a human anti-SARS-CoV-2 pre-spike IgG antibody ELISA (S-ELISA). In brief, the SARS-CoV-2 pre-spike recombinant antigen is adsorbed onto the 96-well microplate. Dilution series of human sera, standard and controls are added to microtitre plates coated with the SARS-CoV-2 pre-spike recombinant antigen. Presence of binding IgGs is detected with an anti-human IgG antibody conjugated to peroxidase, followed by addition of the peroxidase substrate. The optical density of the colored end product is proportional to the amount anti-SARS-CoV-2 pre-spike IgG antibodies present in the serum sample. Values below the quantitation limit of the ELISA (50.3 ELU/mL) and samples scored

as “negative” will be replaced by 25 ELU/mL. Also values above the quantitation limit (>15798 ELU/mL) will be replaced by 15798 ELU/mL.

Immunogenicity analysis will be presented for the respective PPAS and modified PPAS population. In addition analysis can also be presented for FAS population. Immunogenicity analysis may also be presented for “Unscheduled COVID-19 illness visit” that will be performed if a participant tests positive for COVID-19 during the study.

Immunogenicity analysis may also be presented stratified for MNA positive/negative at Visit 1. MNA result will be considered positive if result (ND50) \geq LLOQ, i.e. ≥ 62 . Otherwise if the result (ND50) $<$ LLOQ then MNA will be considered negative.

All secondary immunogenicity analysis for booster phase will be presented by primary treatment group (Low Dose/ Medium Dose/ High Dose) of participant and the tables will also be presented stratified by following factors: Received other COVID-19 vaccine any time during study / Not received other COVID-19 vaccine any time during study/ COVID-19 positive any time during study who did not receive other COVID-19 vaccine any time during study.

Immunogenicity analysis will also be presented for participants in PPAS and mPPAS who received a booster dose.

